**7.1.4.2.8 Day 29 of Course 2 (10-day regimen)**

The observations, examinations, and evaluations listed below will be conducted, and the dates of the conduct and data obtained will be documented in the medical records and CRF.

Clinical Symptoms	Subjective symptoms and objective findings
Vital Signs	Blood pressure (systolic/diastolic), pulse rate, and body temperature
Twelve-lead ECG and chest X-ray	Twelve-lead ECG and chest X-ray
Hematology Test	Hb, Hct, RBC count, WBC count, differential WBC count (visual count: blast cells [leukemia cells], lymphoblastoid cells, monoblasts, promyelocytes, myelocytes, metamyelocytes, segmented neutrophils, stab leucocytes, lymphocytes, eosinophils, monocytes, basophils, prolymphocytes, and promonocytes), platelet count, and reticulocytes
Blood Biochemistry Test	AST (GOT), ALT (GPT), ALP, LDH, TP, ALB, T-Bil, BUN, UA, Cr, blood glucose (fasting), Ca, Mg, Na, K, and Cl
Urinalysis	Bilirubin, occult blood, protein, and urobilinogen
General Condition	ECOG PS

If peripheral blood testing indicates that the subject meets criteria for remission, or if clear disease progression is observed, bone marrow aspiration will be performed.

In principle, each course should consist of 28 days, and if the examination scheduled for Day 29 is performed between Day 26 and Day 28 for example, which is within the acceptable window, IMP administration for the next course should be started on or after Day 29 of the current course.

**7.1.4.2.9 Day 1 of Course 2 (5-day regimen)**

If written informed consent is obtained for extended treatment, the observations, examinations, and evaluations listed below will be conducted before the start of IMP administration on Day 1 of Course 2, and the dates of the conduct and data obtained will be documented in the medical records and CRF. If measurement of vital signs and body weight, hematology test, blood biochemistry test, and urinalysis have been completed within 4 days before Day 1, the available data can be used instead.

Clinical Symptoms	Subjective symptoms and objective findings
Viral Test a	HBV-DNA
Vital Signs	Blood pressure (systolic/diastolic), pulse rate, and body temperature
Body Weight b	Body weight
Hematology Test	Hb, Hct, RBC count, WBC count, differential WBC count (visual count: blast cells [leukemia cells], lymphoblastoid cells, monoblasts, promyelocytes, myelocytes, metamyelocytes, segmented neutrophils, stab leucocytes, lymphocytes, eosinophils, monocytes, basophils, prolymphocytes, and promonocytes), platelet count, and reticulocytes
Blood Biochemistry Test	AST (GOT), ALT (GPT), ALP, LDH, TP, ALB, T-Bil, BUN, UA, Cr, blood glucose (fasting), Ca, Mg, Na, K, and Cl
Urinalysis	Bilirubin, occult blood, protein, and urobilinogen

If peripheral blood testing indicates that the subject meets criteria for remission, or if clear disease progression is observed, bone marrow aspiration will be performed.

a A viral test will be performed only in subjects who are found to be either HBcAB or HBsAB positive at screening.

b Body weight will be measured and the dose of IMP to be administered will be determined according to the calculation of BSA.

**7.1.4.2.10 Day 2 to Day 5 of Course 2 (5-day regimen)**

The observations, examinations, and evaluations listed below will be conducted before the start of IMP administration, and the dates of the conduct and data obtained will be documented in the medical records and CRF.

Clinical Symptoms	Subjective symptoms and objective findings
Vital Signs	Blood pressure (systolic/diastolic), pulse rate, and body temperature

If peripheral blood testing indicates that the subject meets criteria for remission, or if clear disease progression is observed, bone marrow aspiration will be performed.

**7.1.4.2.11 Day 8, Day 15, and Day 22 of Course 2 (5-day regimen)**

The observations, examinations, and evaluations listed below will be conducted, and the dates of the conduct and data obtained will be documented in the medical records and CRF.

Clinical Symptoms	Subjective symptoms and objective findings
Vital Signs	Blood pressure (systolic/diastolic), pulse rate, and body temperature
Hematology Test	Hb, Hct, RBC count, WBC count, differential WBC count (visual count: blast cells [leukemia cells], lymphoblastoid cells, monoblasts, promyelocytes, myelocytes, metamyelocytes, segmented neutrophils, stab leucocytes, lymphocytes, eosinophils, monocytes, basophils, prolymphocytes, and promonocytes), platelet count, and reticulocytes

If peripheral blood testing indicates that the subject meets criteria for remission, or if clear disease progression is observed, bone marrow aspiration will be performed.

**7.1.4.2.12 Day 29 of Course 2 (5-day regimen)**

The observations, examinations, and evaluations listed below will be conducted, and the dates of the conduct and data obtained will be documented in the medical records and CRF.

Clinical Symptoms	Subjective symptoms and objective findings
Vital Signs	Blood pressure (systolic/diastolic), pulse rate, and body temperature
Twelve-lead ECG and chest X-ray	Twelve-lead ECG and chest X-ray
Hematology Test	Hb, Hct, RBC count, WBC count, differential WBC count (visual count: blast cells [leukemia cells], lymphoblastoid cells, monoblasts, promyelocytes, myelocytes, metamyelocytes, segmented neutrophils, stab leucocytes, lymphocytes, eosinophils, monocytes, basophils, prolymphocytes, and promonocytes), platelet count, and reticulocytes
Blood Biochemistry Test	AST (GOT), ALT (GPT), ALP, LDH, TP, ALB, T-Bil, BUN, UA, Cr, blood glucose (fasting), Ca, Mg, Na, K, and Cl
Urinalysis	Bilirubin, occult blood, protein, and urobilinogen
General Condition	ECOG PS

If peripheral blood testing indicates that the subject meets criteria for remission, or if clear disease progression is observed, bone marrow aspiration will be performed.

In principle, each course should consist of 28 days, and if the examination scheduled for Day 29 is performed between Day 26 and Day 28 for example, which is within the acceptable window, IMP administration for the next course should be started on or after Day 29 of the current course.

**7.1.4.2.13 Day 1 of Course 3 and Subsequent Courses (5-day regimen)**

The observations, examinations, and evaluations listed below will be conducted before the start of IMP administration on Day 1 of Course 3, and the dates of the conduct and data obtained will be documented in the medical records and CRF. If measurement of

vital signs and body weight, hematology test, blood biochemistry test, and urinalysis have been completed within 4 days before Day 1, the available data can be used instead.

Clinical Symptoms	Subjective symptoms and objective findings
Viral Test a	HBV-DNA
Vital Signs	Blood pressure (systolic/diastolic), pulse rate, and body temperature
Body Weight b	Body weight
Hematology Test	Hb, Hct, RBC count, WBC count, differential WBC count (visual count: blast cells [leukemia cells], lymphoblastoid cells, monoblasts, promyelocytes, myelocytes, metamyelocytes, segmented neutrophils, stab leucocytes, lymphocytes, eosinophils, monocytes, basophils, prolymphocytes, and promonocytes), platelet count, and reticulocytes
Blood Biochemistry Test	AST (GOT), ALT (GPT), ALP, LDH, TP, ALB, T-Bil, BUN, UA, Cr, blood glucose (fasting), Ca, Mg, Na, K, and Cl
Urinalysis	Bilirubin, occult blood, protein, and urobilinogen

If peripheral blood testing indicates that the subject meets criteria for remission, or if clear disease progression is observed, bone marrow aspiration will be performed.

a A viral test will be performed only in subjects who are found to be either HBcAB or HBsAB positive at screening.

b Body weight will be measured and the dose of IMP to be administered will be determined according to the calculation of BSA.

#### 7.1.4.2.14 Day 2 to Day 5 of Course 3 and Subsequent Courses (5-day regimen)

The observations, examinations, and evaluations listed below will be conducted before the start of IMP administration, and the dates of the conduct and data obtained will be documented in the medical records and CRF.

Clinical Symptoms	Subjective symptoms and objective findings
Vital Signs	Blood pressure (systolic/diastolic), pulse rate, and body temperature

If peripheral blood testing indicates that the subject meets criteria for remission, or if clear disease progression is observed, bone marrow aspiration will be performed.

#### 7.1.4.2.15 Day 15 of Course 3 and Subsequent Courses (5-day regimen)

The observations, examinations, and evaluations listed below will be conducted, and the dates of the conduct and data obtained will be documented in the medical records and CRF.

Clinical Symptoms	Subjective symptoms and objective findings
Vital Signs	Blood pressure (systolic/diastolic), pulse rate, and body temperature
Hematology Test	Hb, Hct, RBC count, WBC count, differential WBC count (visual count: blast cells [leukemia cells], lymphoblastoid cells, monoblasts, promyelocytes, myelocytes, metamyelocytes, segmented neutrophils, stab leucocytes, lymphocytes, eosinophils, monocytes, basophils, prolymphocytes, and promonocytes), platelet count, and reticulocytes

If peripheral blood testing indicates that the subject meets criteria for remission, or if clear disease progression is observed, bone marrow aspiration will be performed.

**7.1.4.2.16 Day 29 of Course 3 and Subsequent Courses (5-day regimen)**

The observations, examinations, and evaluations listed below will be conducted, and the dates of the conduct and data obtained will be documented in the medical records and CRF.

Clinical Symptoms	Subjective symptoms and objective findings
Vital Signs	Blood pressure (systolic/diastolic), pulse rate, and body temperature
Twelve-lead ECG and chest X-ray	Twelve-lead ECG and chest X-ray
Hematology Test	Hb, Hct, RBC count, WBC count, differential WBC count (visual count: blast cells [leukemia cells], lymphoblastoid cells, monoblasts, promyelocytes, myelocytes, metamyelocytes, segmented neutrophils, stab leucocytes, lymphocytes, eosinophils, monocytes, basophils, prolymphocytes, and promonocytes), platelet count, and reticulocytes
Blood Biochemistry Test	AST (GOT), ALT (GPT), ALP, LDH, TP, ALB, T-Bil, BUN, UA, Cr, blood glucose (fasting), Ca, Mg, Na, K, and Cl
Urinalysis	Bilirubin, occult blood, protein, and urobilinogen
General Condition	ECOG PS

If peripheral blood testing indicates that the subject meets criteria for remission, or if clear disease progression is observed, bone marrow aspiration will be performed.

In principle, each course should consist of 28 days, and if the examination scheduled for Day 29 is performed between Day 26 and Day 28 for example, which is within the acceptable window, IMP administration for the next course should be started on or after Day 29 of the current course.

**7.1.4.2.17 Day 1 to Day 29 of the Extended Course in the Extended Treatment Part**

The observations, examinations, and evaluations listed below will be conducted before the start of IMP administration on Day 1 of each course and during each course, and the dates of the conduct and data obtained will be documented in the medical records. In addition, examinations related to safety will be performed as necessary, and the dates of the conduct and data obtained will be documented in the medical records.

Clinical Symptoms	Subjective symptoms and objective findings
Hematology Test	Hb, Hct, RBC count, WBC count, differential WBC count (visual count: blast cells [leukemia cells], lymphoblastoid cells, monoblasts, promyelocytes, myelocytes, metamyelocytes, segmented neutrophils, stab leucocytes, lymphocytes, eosinophils, monocytes, basophils, prolymphocytes, and promonocytes), platelet count, and reticulocytes

**7.1.5 Observations, Examinations, and Evaluations at the Time of Withdrawal**

The observations, examinations, and evaluations listed below will be conducted within 5 days after withdrawal from the trial has been decided, and the dates of the conduct and

data obtained will be documented in the medical records and CRF. If the withdrawal examination takes place within the acceptable time window for Day 8, Day 15, Day 22, or Day 29, it is not necessary to repeat items that have been performed in the examinations for Day 8, Day 15, Day 22, or Day 29 for the withdrawal examination. If the withdrawal is due to an SAE or progression of the primary disease, only those examinations that are feasible, given the subject’s state of health, will be performed in consideration of the subject’s conditions.

Clinical Symptoms	Subjective symptoms and objective findings
Pregnancy Test a	Urinary or serum HCG
Vital Signs	Blood pressure (systolic/diastolic), pulse rate, and body temperature
Body Weight	Body weight
Twelve-lead ECG and chest X-ray	Twelve-lead ECG and chest X-ray
Hematology Test	Hb, Hct, RBC count, WBC count, differential WBC count (visual count: blast cells [leukemia cells], lymphoblastoid cells, monoblasts, promyelocytes, myelocytes, metamyelocytes, segmented neutrophils, stab leucocytes, lymphocytes, eosinophils, monocytes, basophils, prolymphocytes, and promonocytes), platelet count, and reticulocytes
Blood Biochemistry Test	AST (GOT), ALT (GPT), ALP, LDH, TP, ALB, T-Bil, BUN, UA, Cr, blood glucose (fasting), Ca, Mg, Na, K, and Cl
Urinalysis	Bilirubin, occult blood, protein, and urobilinogen
General Condition	ECOG PS
Bone Marrow Aspiration b	Percentage of bone marrow fluid (blasts, lymphoblasts, monoblasts, promyelocytes, myelocytes, metamyelocytes, segmented neutrophils, stab leucocytes, lymphocytes, eosinophils, monocytes, basophils, normoblasts, pronormoblasts, erythroblasts, plasma cells, and megakaryocytes), M/E ratio, and cellularity

HCG = Human chorionic gonadotropin

a A pregnancy test will be performed in female subjects at the trial site. However, a pregnancy test is not required for subjects who have undergone bilateral oophorectomy or hysterectomy, or subjects who have been amenorrheic without a medical cause for at least 12 consecutive months.

b If peripheral blood testing indicates that the subject meets criteria for remission, or if clear disease progression is observed, bone marrow aspiration will be performed.

## 7.2 Method of Evaluation

### 7.2.1 Safety Evaluation (Primary Evaluation Part)

#### 7.2.1.1 Clinical Symptoms

The investigator or subinvestigator will examine subjects at the timepoints stipulated in the protocol, and record subjective symptoms and objective findings that are deemed to be AEs in the CRF.

### **7.2.1.2 Dose Limiting-toxicities and Adverse Events**

Dose limiting-toxicities and AEs will be assessed in accordance with the CTCAE version 4.0. See the sections on AEs for details.

Occurrence of DLTs will be recorded in the CRF in a timely manner after the end of the DLT evaluation period, and if any DLT occurs, detailed information of the DLT (date of onset, severity, seriousness, outcome, and relationship with the IMP) as well as the status of IMP administration in Course 1 will be also recorded in the CRF. In Course 2 and subsequent courses as well, detailed information of any DLTs will be recorded in the CRF.

### **7.2.1.3 Body Weight**

Body weight will be measured in accordance with the procedures specified at the trial site, and the date of measurement and data obtained will be documented in the medical records and CRF.

### **7.2.1.4 General Condition**

Each subject's general condition will be assessed by reference to the Japanese version of the ECOG PS, and the date of assessment and assessment results will be documented in the medical records and CRF. Death will be scored as 5.

0	Fully active, able to carry on all pre-disease performance without restriction.
1	Restricted in physically strenuous activity but ambulatory and able to carry out work of a light or sedentary nature, e.g., light house work, office work.
2	Ambulatory and capable of all self-care but unable to carry out any work activities. Up and about more than 50% of waking hours.
3	Capable of only limited self-care, confined to bed or chair more than 50% of waking hours.
4	Completely disabled. Cannot carry on any self-care. Totally confined to bed or chair.

These criteria are indices for general condition. Activity restricted because of local symptoms should be based on clinical judgment.

Source: Common Toxicity Criteria Version 2.0 published on 30 April 1999

([http://ctep.cancer.gov/protocolDevelopment/electronic\\_applications/docs/ctcv20\\_4-30-992.pdf](http://ctep.cancer.gov/protocolDevelopment/electronic_applications/docs/ctcv20_4-30-992.pdf));

website of Japan Clinical Oncology Group (<http://www.jcog.jp/>)

### **7.2.1.5 Vital Signs (Blood Pressure, Pulse Rate, and Body Temperature)**

Blood pressure (systolic/diastolic), pulse rate, and body temperature will be measured (in the sitting position after 3-minute rest), and the date of measurement and data obtained will be documented in the medical records and CRF.

### **7.2.1.6 Twelve-lead Electrocardiogram**

Twelve-lead ECG will be performed in accordance with the procedures specified at the trial site. A central ECG reading facility will analyze heart rate, PR interval, RR interval,

QRS interval, QT interval, and corrected QT interval (QTc interval). The QT interval (QT interval as corrected by Fridericia’s formula [QTcF interval]) will be calculated using the following formula:  $QTcF = (QT \text{ interval} / RR \text{ interval})^{1/3}$ . The central ECG reading facility will report analysis results to the investigator or subinvestigator. Then, the investigator or subinvestigator will check the results, and sign the analysis report and enter the date of confirmation. The investigator or subinvestigator will decide whether the ECG is normal or abnormal based on the analysis results submitted by the central ECG reading facility, and will document the decision and the date and time of the examination in the medical records and CRF. Clinically significant findings will be assessed as AEs.

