## List of Abbreviations and Definition of Terms

### List of Abbreviations

Abbreviation	Expansion
ADL	Activities of daily living
AE	Adverse event
ALB	Albumin
ALP	Alkaline phosphatase
ALT	Alanine aminotransferase
AML	Acute myeloid leukemia
APL	Acute promyelocytic leukemia
AST	Aspartate aminotransferase
BED	Biologically effective dose
BSA	Body surface area
BUN	Blood urea nitrogen
BW	Body Weight
CMML	Chronic myelomonocytic leukemia
Cr	Creatinine
CR	Complete remission
CRF	Case report form
CRi	Complete remission with incomplete blood count recovery
CRp	Complete remission with incomplete platelet recovery
CSR	Clinical study report
CTCAE	Common Terminology Criteria for Adverse Events
CYP	Cytochrome P-450
DLCO	Diffusing capacity of the lung for carbon monoxide
DLT	Dose-limiting toxicity
DNMT	DNA methyltransferase
ECG	Electrocardiogram, electrocardiography
ECOG	Eastern Cooperative Oncology Group
EDC	Electronic data capture
EDTA	Ethylenediaminetetraacetic acid
FEV 1	Forced expiratory volume in the first second
GOT	Glutamate oxaloacetate transaminase
GPT	Glutamate pyruvate transaminase
GVHD	Graft-versus host disease
Hb	Hemoglobin
HBcAB	Hepatitis B core antibody
HBsAB	Hepatitis B surface antibody
HBV	Hepatitis B virus
HCG	Human chorionic gonadotropin
Hct	Hematocrit
HCV	Hepatitis C virus
hERG	Human ether-a-go-go related gene
HI-E	Hematological improvement of erythrocytes
HI-P	Hematological improvement of platelets
HIV	Human immunodeficiency virus
HNSTD	Highest non-severely toxic dose
ICF	Informed consent form
ICH	International Conference on Harmonisation of Technical Requirements for Registration of Pharmaceuticals for Human Use

Abbreviation	Expansion
IMP	Investigational medicinal product
IRB	Institutional Review Board
LDH	Lactate dehydrogenase
LINE-1	Long interspersed nucleotide element-1
LVEF	Left ventricular ejection fraction
M/E ratio	Myeloid/erythroid ratio
mCR	Marrow complete remission
MDS	Myelodysplastic syndrome
MTD	Maximum tolerated dose
MUGA	Multiple-gated acquisition
NE	Not evaluable
NOEL	No observed effect level
NYHA	New York Heart Association
PD	Pharmacodynamic(s)
PK	Pharmacokinetic(s)
PR	Partial response
PS	Performance status
PT	Preferred term
QTc interval	Corrected QT interval
QTcF interval	QT interval as corrected by Fridericia's formula
RBC	Red blood cell
SAE	Serious adverse event
SC	Subcutaneous(ly)
SOC	System organ class
T-Bil	Total bilirubin
TP	Total protein
UA	Uric acid
ULN	Upper limit of normal
US	United States

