## **10 Collection of Case Report Form Data and Specification of Source Data**

### **10.1 Collection of Case Report Form Data**

- 1) Electronic Data Capture (EDC) will be used in the primary evaluation part of the trial, and the paper CRF will be used in the extended treatment part for data collection.
- 2) Subject data will be entered directly into the database from the trial site via a Web browser. These data collected by EDC will constitute the CRF. The 12-lead ECG analysis results obtained from the ECG reading facility (central ECG reading facility) will be transferred from the ECG measurement facilities directly to the sponsor.
- 3) Regarding quality assurance of CRFs, the guidelines specified in "Use of Electromagnetic Records and Electronic Signatures in Applications for Approval or Licensing of Drugs" (PFSB Notification No. 0401022, dated 01 Apr 2005) and

“Guidance on Electronic Capture of Clinical Study Data” (Drug Evaluation Committee, Japan Pharmaceutical Manufacturers Association, dated 01 Nov 2007) will be observed

- 4) For every subject who provides consent to participate in the trial, a CRF will be created on an EDC data entry screen that conforms to the items of CRF data collection described in the trial protocol.
- 5) The investigator, subinvestigator, or trial associate will create CRFs according to the manual provided by the sponsor. If source documents are available and the objectivity of the data can be ensured, then the data may be recorded in a CRF by a trial associate.
- 6) When entering data into CRFs from the trial site, a predetermined check will be automatically performed. The investigator, subinvestigator, or a trial associate will make corrections as necessary.
- 7) The sponsor will verify CRFs in comparison to source documents and conduct data reviews. If additional query is necessary, the sponsor will issue an intra-system query and the investigator, subinvestigator, or a trial associate will perform data correction or provide a response to the sponsor’s query as necessary.
- 8) A history of all revisions made after the initial data entry is saved on the server will be automatically recorded within the system (date and time of revision, name of person making revision, pre- and post-revision data, reason for revision, date and time of query, name of person issuing query, details of query, etc).

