### **10.4 Data to Be Collected by the Sponsor**

- 1) CRFs (data following acquisition of informed consent)
- 2) Clinical laboratory results and reference values
- 3) Copies of results of drug concentration measurement
- 4) Copies of results of PD measurement
- 5) Copies of ECG charts
- 6) 12-lead ECG analysis report

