Heart rate, PR interval, RR interval, QRS interval, QT interval, and QTcF interval, at each timepoint will be summarized by cohort as follows:

- Descriptive statistics of measurements
- Descriptive statistics of change from baseline

QTcF interval at the last evaluation and the worst value (maximum value after the start of treatment) will be summarized by cohort.

- The number and percentage of subjects with a measured value > 450 ms, > 480 ms, or > 500 ms will be calculated.
- The number and percentage of subjects with change > 30 ms or > 60 ms will be calculated.

Assessment of ECG abnormalities (normal or abnormal) at each timepoint will be summarized by cohort as follows:

- A shift table of data from baseline

- f) Chest X-ray

Assessment of chest X-ray abnormalities (normal or abnormal) at each timepoint will be summarized by cohort as follows:

- A shift table of data from baseline

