9.3.5 ECG (12-Lead ECG)

Electrocardiographic (ECG) assessment by site investigator will be used for the analysis.

The following items will be tabulated for heart rate, PR interval, RR interval, QRS interval, QT interval, and QT interval as corrected by Fridericia's formula (QTcF interval) at each time point.

- Descriptive statistics of the measured values
- Descriptive statistics of the change from baseline

The number of subjects and incidence of the following items will be tabulated by cohort for QTcF interval of last value and worst value (maximum value obtained after the start of IMP administration).

- Measured values will be classified as "greater than 450 ms", "greater than 480 ms", and "greater than 500 ms" for tabulation.
- Changes from baseline will be classified as "greater than 30 ms" and "greater than 60 ms" for tabulation.

The following item will be tabulated by cohort using the normality judgment (normal or abnormal) for the electrocardiogram at each time point.

- Shift table from baseline

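### The printed QTcF formula puts QT inside the cube root, so no value it gives can reach the planned millisecond cut-offs

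*Protocol*

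**What the plan says.** Protocol 7.2.1.6 has a central ECG reading facility analyse heart rate and the PR, RR, QRS, QT and QTc intervals. It states that the Fridericia-corrected value is to be computed from a formula, which it prints as "QTcF = (QT \text{ interval} / RR \text{ interval})^{1/3". The closing bracket comes before the exponent, so the power of 1/3 applies to QT divided by RR. No unit is given for either interval.

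The abbreviation list defines QTcF as "QT interval as corrected by Fridericia's formula" and gives no formula. SAP 9.3.5 also names Fridericia without a formula, and SAP section 13, on changes from the protocol, does not mention QTcF. The formula in Protocol 7.2.1.6 is therefore the only one in either document.

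The analyses use QTcF in milliseconds. Protocol 11.3.1.2 e) states: "The number and percentage of subjects with a measured value > 450 ms, > 480 ms, or > 500 ms will be calculated", and for change from baseline: "The number and percentage of subjects with change > 30 ms or > 60 ms will be calculated". SAP 9.3.5 repeats the same cut-offs, to be "tabulated by cohort for QTcF interval of last value and worst value (maximum value obtained after the start of IMP administration").

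On data flow, Protocol 10.1 says the central ECG results "will be transferred from the ECG measurement facilities directly to the sponsor", and the list in Protocol 10.4 of what the sponsor collects includes the "12-lead ECG analysis report".

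**The concern.** Fridericia's correction divides QT by the cube root of RR, with QT outside the root. The printed version takes the cube root of QT as well. That conflicts with the method named in the same sentence, and with analyses that need a value in milliseconds.

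Twelve-lead ECG is a secondary safety endpoint, and QTcF is the only ECG interval with categorical cut-offs. If the printed rule were programmed, every subject would fall below every cut-off. Subjects whose true QTcF is 450 ms or less would still be placed correctly, but every true exceedance would be missed, and the QTcF means and changes could not be interpreted. The summaries of uncorrected QT, RR and heart rate would not be affected.

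**Working it through.** Neither document gives a worked QTcF value, so there is no figure to reproduce. The check evaluates the printed formula and the Fridericia form on the same inputs.

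**Inputs from the documents:** the printed formula (Protocol 7.2.1.6); cut-offs of 450, 480 and 500 ms, and changes of 30 and 60 ms (Protocol 11.3.1.2 e, SAP 9.3.5).

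**Assumed inputs:** QT 360–520 ms and RR 600–1000 ms. A much wider grid, QT 200–800 ms by RR 250–2500 ms, serves as a stress test.

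**Formulas**

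- Printed: (QT/RR)^(1/3). With both intervals in one unit the result has no unit. With QT in ms and RR in s it is 1000^(1/3) = 10 times larger.
- Fridericia: QT (ms) / [RR (s)]^(1/3), in ms.

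**Range**

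- Printed, same unit: (360/1000)^(1/3) = 0.711 to (520/600)^(1/3) = 0.953.
- Printed, QT in ms and RR in s: (360/1.0)^(1/3) = 7.11 to (520/0.6)^(1/3) = 9.53.
- Fridericia: 360/(1.0)^(1/3) = 360.0 ms to 520/(0.6)^(1/3) = 616.5 ms.
- Largest change the printed form can show: 0.953 − 0.711 = 0.242, or 2.42 in mixed units.

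**Individual ECGs at RR 800 ms**

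| QT (ms) | Printed, same unit | Printed, ms and s | Fridericia (ms) | True category |
|---|---|---|---|---|
| 400 | 0.794 | 7.94 | 430.9 | not above 450 |
| 440 | 0.819 | 8.19 | 474.0 | above 450 |
| 470 | 0.838 | 8.38 | 506.3 | above 500 |

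If QT rises from 400 to 470 ms, the true change is 506.3 − 430.9 = 75.4 ms, which is above 60 ms. The printed form shows 0.044, or 0.438 in mixed units.

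**Stress test.** On the wide grid the printed form runs from 0.43 to 1.47 (largest difference 1.04), or from 4.31 to 14.74 in mixed units (largest difference 10.43).

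**What the cut-offs would require.** For the printed value to exceed 450, QT/RR would have to exceed 450³ = 91,125,000. Even a value of 30 needs QT/RR = 30³ = 27,000. No ECG comes near either.

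**Unit of RR.** Moving the bracket is not enough if the unit stays unstated. With QT 400 ms and RR 800 ms, the Fridericia form gives 430.9 ms with RR in seconds, but 43.1 if RR is entered in milliseconds.

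**The case against.** The strongest reply is that the formula may never be used. Fridericia is named beside it and again in the SAP, the cut-offs are in milliseconds, and a central facility does the reading. Values near 0.8 in a column headed in milliseconds would probably be noticed at once. Nothing in the documents shows that any QTcF was computed this way. This stands, and it limits the practical risk. It does not make the printed calculation rule correct.

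Second, the bracket may have shifted when the PDF was converted to text. This cannot be ruled out from the text alone, so the correction depends on checking the page.

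Third, the error need not always hide exceedances. If both intervals were entered in seconds and the result were read as seconds, 0.40/1.00 would give 0.737, taken as 737 ms, and a true 400 ms would be counted above 500. That requires a further mistake, treating a unitless ratio as a time. The statement about missed exceedances refers to the formula taken at face value.

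Fourth, little depends on QTcF. It is a descriptive secondary summary in at most 24 subjects, with no tests or intervals. It is not named in the eligibility, dose-limiting toxicity or withdrawal criteria, and it can be recomputed from QT and RR. All of this is correct. It is why the point is a correction to make rather than a threat to the trial's main conclusion.

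**Conclusion.** The concern holds. As the text reads, the only QTcF formula in the plan contradicts both the named correction and the units of the planned tables. Applied literally, it gives zero counts in all five QTcF categories whatever the data, because its values stay below 15 even on the wide assumed grid. An ECG with a true QTcF of 474 ms, or a true rise of 75 ms, would not be counted.

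This rests on two conditions: that the bracket is placed in the PDF as in the extracted text, and that someone follows the formula rather than the method's name. The QT and RR ranges are assumed, but the conclusion does not depend on them, given the QT/RR ratios the cut-offs would require. The primary analysis of dose-limiting toxicity does not use the QTcF cut-offs.

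**What to change.** 1. Compare the bracket in Protocol 7.2.1.6 with the protocol PDF.
2. If it is as extracted, replace the formula with QTcF (ms) = QT (ms) / [RR (s)]^(1/3), stating both units.
3. Print the same formula in SAP 9.3.5, so that the programmer has it in the document being worked from.
4. Ask the central reading facility to confirm in writing that its QTcF values used this form. This should include Cohorts 1, 2 and 4, whose interim lock SAP section 4 dates to 25 Aug 2017. If it did not use this form, recompute from QT and RR.

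As an optional and separate clarification, SAP 9.3.5 says the site investigator's ECG assessment will be used, while the protocol sends central results to the sponsor. The SAP could state that the interval values come from the central reading and that the investigator's assessment supplies the normal/abnormal shift table.

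The cost is one line in each document and one confirmation, with no new data. Because a protocol change carries the agreement and review steps in Protocol 13.6, the SAP line and the confirmation can come first, before database lock, and the protocol line can follow at the next amendment.
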